10.2 Post-treatment Sample Collection

- Collection of peritoneal fluid after ketorolac administration will be done at select time-points after ketorolac administration (1 hour, 6 hours, and 24 hours) an additional 48 hour sample (after the initial dose) will be done in patients having elective multiple ketorolac dosing.
- Cells and effluent will be separated from fluid at the above select time-points (1 hour, 6 hours, 24 hours) and at 48 hours after the initial ketorolac dose in patients who receive elective multiple ketorolac dosing.

10.3 Pharmacokinetic Evaluation:

Blood and 10-20 ccs of peritoneal fluid will be retrieved at the following time-points. Serum will be isolated and peritoneal fluid will be isolated from cellular material via centrifugation.

Timepoint	Time after ketorolac
1	Predose
2	1 hour
3	6 hours
4	24 hours
5	48 hours*

* elective time-point for patients receiving clinically indicated multiple dosing of ketorolac

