11.2 Endpoint Analyses

11.2.1 Primary Endpoint and Sample Size

Ketorolac availability, concentration and racemic mixture of Toradol® ([R,S]-ketorolac) in the peritoneal cavity. Intraperitoneal concentration and racemic mixture of ketorolac is currently unknown although serum pharmacokinetic data suggests a slower clearance of the R-racemate. The **primary objective** of this study is to determine the concentration of measurable levels of R and S- Ketorolac (and the percent racemic mixture) in the peritoneal cavity after IV administration in the post-operative patient after cytoreductive surgery. Since this is a pilot trial for feasibility of obtaining the desired measures, a true sample size calculation is difficult to assess. We anticipate that we will need to recruit 60 patients pre-operatively who meet the first phase of eligibility. We anticipate that 60% will have a diagnosis other than advanced stage invasive epithelial ovarian cancer, fail optimal debulking, have a clinical decision to not proceed with a port placement or not enough ascites or negative cytology of the ascites that will warrant no further participation in the study. This data is based on our initial experience with the first 12 patients enrolled on the trial. We then anticipate that 25 patients will have intraoperative port placement and be eligible for secondary eligibility. We anticipate that an additional 15-18 patients will either fail secondary eligibility, decline sample collection, decline ketorolac or have indications to withhold ketorolac, decline blood sampling, have inadequate re-accumulated fluid for sampling, or failed extraction of ascites samples from the port. The sample target remains 7-10 complete sets of blood and ascites samples for primary and secondary endpoint analyses.

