11.2.2 Secondary Endpoints

We will determine the effect of IV ketorolac on cell adhesion and migration on ovarian cancer cells retrieved from the peritoneal cavity after cytoreductive surgery using several different biologic assays. Isolated cells will be tested for evidence of target inhibition and functional changes in adhesion and migration. Target activity assays: Rac1 and Cdc42 activity will be measured in cells using effector binding assays (GLISA) that are

commercially available (Cytoskeleton, Inc) and are used to determine activity of primary cells ex vivo as we have demonstrated in (Fig. 1C). In addition, we will conduct qRT-PCR analysis of cells isolated pre and post ketorolac administration to test for expression of genes downstream of Rac1 and Cdc42 activation that were validated in cell culture and in vivo studies. Adhesive properties of cells will be measured by assays for spreading and adhesion. For spreading analysis, cells will be rinsed in Dulbecco's PBS (DPBS) and plated on coverslips without or with extracellular matrix coating and images will be obtained at regular intervals. Spreading is defined as flattened cells without the refractile, fibroblastic morphology determined and expressed as a percentage of the total cells \pm SD as we've described previously (46). For adhesion, cells will be plated onto 96 well plates without or with extracellular matrix coating and incubated for 30 min. Cells will be fixed and non-adherent cells will be removed by gentle washing. Colorimetric quantification of adherent cells will be performed using standard protocols. Migration will be measured after plating cells on collagen-coated coverslips in assessing migration by time lapse photography on a heated microscope stage (UNM Microscopy Facility). Distance traversed for individual cells will be quantified by image analysis software. Data will be analyzed as a repeated measure ANOVA followed by Tukey's post hoc analysis in order to evaluate whether there are significant differences between groups (pre-and post-ketorolac treatment). Trend analyses of response will also be performed based on peritoneal R-ketorolac concentrations.

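### Repeated-measures ANOVA with all-pairs Tukey does not fit the pre/post question: it cannot show a low 24 h ketorolac level, and for the cell assays it allocates error unevenly between times

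*Combined protocol and SAP*

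**What the plan says.** Section 11.2.1 (primary) and Section 11.2.2 (secondary) use the same sentence: "Data will be analyzed as a repeated measure ANOVA followed by" Tukey's post hoc test. Its stated purpose is to look for "significant differences between groups (pre-and post-ketorolac treatment").

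Blood and peritoneal fluid are taken predose and at "1 hour, 6 hours, and 24 hours" (Section 10.2). The 48 h sample is an "elective time-point for patients receiving clinically indicated multiple dosing of ketorolac". Predose is the reference: Section 10.3.4 lists pre-treatment cells as a control, and Section 10.3.5 compares each treatment time with time zero.

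On size, "The sample target remains 7-10 complete sets of blood and ascites samples". The two dose groups are to be analysed together (Section 11.2.1). The plan names no alpha, error term, sphericity correction, transformation or planned contrasts.

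**The concern.** Four times give 4×3/2 = 6 Tukey pairs, of which only 3 involve predose. The other three compare post-dose times with each other and lie outside the stated question. With 48 h included there would be 10 pairs, 4 of them against predose, and a complete-case ANOVA could not include that time for everyone.

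The larger issue is the error term. Repeated-measures ANOVA followed by Tukey normally applies one pooled subject-by-time error to every pair. That is correct only if the difference between any two times has the same variance (sphericity). If not, contrasts involving a noisy time are judged against too small an error, and contrasts between quiet times against too large a one. At stake are a false claim at a noisy time and, more seriously here, a report of no significant difference from predose at a time when drug is measurable. Measurable peritoneal levels are the primary objective (Section 2.1).

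**Working it through.** **The plan's own figures.** Section 11.2.1 says "we will need to recruit 60 patients pre-operatively" and expects to lose 60% at the first stage: 60 × 0.40 = 24, against 25 stated. Then 25 − 15 = 10 and 25 − 18 = 7, which is the target. There is no power calculation to reproduce. I assume two-sided 0.05 throughout.

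**Critical values at n=7.** Tukey, 4 times, 18 df: 2.83. Holm over three paired contrasts, 6 df: 3.29 at the first step and 2.45 at the last.

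**Concentrations.** Inputs from Section 1.5.2, all serum values: single-dose Cmax 4.65 (SD 0.7) mcg/mL at 30 mg and 2.47 (SD 0.51) at 15 mg; R half-life 5 h (SD 1.7). Section 4.2 excludes prior NSAID use, so predose is set to 0. Assumptions: serum stands in for peritoneal fluid, one dose only, a 50:50 dose mix, R equal to half of Cmax, and level = (Cmax/2) × 2^(−t/half-life).

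- Simulated R levels: mean 0, 1.52, 0.73 and 0.08 mcg/mL; SD 0, 0.55, 0.36 and 0.08, at predose, 1, 6 and 24 h.
- Variances of the six differences: predose–1 h 0.30, predose–6 h 0.13, predose–24 h 0.006, 1–6 h 0.09, 1–24 h 0.26, 6–24 h 0.09. Sphericity would make these equal; the largest is about 50 times the smallest.
- Their mean is 0.876/6 = 0.146, so the pooled error is 0.146/2 = 0.073.
- Smallest difference Tukey can declare at n=7: 2.83 × √(2 × 0.073/7) = 0.41 mcg/mL. At n=10 (critical value 2.74): 2.74 × √(0.146/10) = 0.33. The 24 h mean is 0.08.
- The 24 h contrast's own standard error at n=7: 0.076/√7 = 0.029, so the typical t is 0.079/0.029 = 2.7. The 1 and 6 h contrasts almost always pass, so Holm tests 24 h against 2.45.
- Chance of declaring 24 h different from predose at n=7: Tukey about 0%; Holm-adjusted paired about 73% (71% to 77% depending on the distribution assumed for half-life).

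The mean of 0.08 lies above the lowest HPLC standard of 0.025 mcg/mL (Section 10.3.1), though about 28% of individual R values fall below that standard. For S (half-life 2.5 h) nearly all 24 h values do.

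**Cell assays.** No SDs or correlations by time are given, so the patterns below are assumptions. Simulated with no true change, n=7, 40,000 trials each; percentages of trials with a false positive:

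| SD at predose, 1, 6, 24 h | Correlation | Any of 6 pairs | Any of 3 v predose | 1 h | 6 h | 24 h | Holm paired, any |
|---|---|---|---|---|---|---|---|
| 1, 1, 1, 1 | equal 0.5 | 5.1 | 3.1 | 1.2 | 1.2 | 1.1 | 4.7 |
| 1, 1.5, 1.5, 1 | AR(1) 0.5 | 5.4 | 3.0 | 0.7 | 2.0 | 0.7 | 4.8 |
| 1, 1, 1.25, 1.5 | AR(1) 0.5 | 6.2 | 4.4 | 0.1 | 1.2 | 3.6 | 4.6 |
| 1, 1, 2, 3 | AR(1) 0.5 | 7.5 | 5.5 | 0.0 | 0.6 | 5.1 | 4.6 |
| 1, 1, 1, 3 | AR(1) 0.5 | 9.5 | 7.5 | 0.0 | 0.0 | 7.5 | 4.6 |
| 1, 3, 2, 1 | AR(1) 0.5 | 7.0 | 3.5 | 3.1 | 0.6 | 0.0 | 4.7 |
| 1, 1, 1, 1 | AR(1) 0.8 | 6.8 | 5.7 | 0.4 | 2.3 | 4.5 | 4.4 |

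If predose itself is three times as variable (equal correlation 0.5), all-pairs error is 9.3%, all of it on the predose contrasts. Ten patients give nearly the same rates.

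**Power at n=7, true shift of 1.5 baseline SDs, Tukey against Holm paired.**
- Shift at 1 h only: SDs 1, 1, 2, 3 give 7% v 73%; SDs 1, 1, 1.25, 1.5 give 54% v 73%; SDs 1, 3, 2, 1 give 21% v 11%.
- Equal SDs, equal correlation 0.5: 86% v 73% for a shift at one time, 86% v 78% at two, 86% v 84% at all three. At n=10 the one-time case is 97% v 94%.

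**The case against.** The strongest reply is that this is a pilot. Its primary objective is an estimate, no go/no-go rule hangs on these p-values, PCR has its own fold-change criterion, and the pooled error is inferred because the plan names none. All of that stands and limits the consequence. It does not remove the point: both sections plan significance tests, and Section 11.2.1 claims that seven patients give statistically meaningful results.

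Three stronger readings are tempting, and the documents do not support them.

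- *That Tukey generally inflates false positives for the stated question.* On the three predose contrasts, family error is about 2.5–7.5% across patterns where a post-dose time is noisiest. It exceeds that range only if predose is the noisy time.
- *That late times are noisy, giving false positives at 24 h and missed effects at 1 h.* No assay SDs are given. For single-dose concentrations the half-lives point the other way, since 24 h is 24/5 = 4.8 R half-lives and 24/2.5 = 9.6 S half-lives. With early noise, Tukey does better than paired contrasts at 1 h (21% v 11%).
- *That a predose with almost no variance is enough to break the test.* SDs of 0.05, 1, 1, 1 at correlation 0.5 left all-pairs error at 5.0%. What matters is unequal variance of the differences.

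The objection that paired contrasts are not free also stands. Each has 6 df instead of 18 at n=7.

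**Conclusion.** The point holds, more firmly for concentrations than for the assays.

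For concentrations, confidence is high that the equal-variance assumption fails for single-dose samples, because the documents supply the pattern. The size (about 0% against 73% at 24 h) rests on the serum stand-in. Section 1.5.2 says peritoneal distribution is unknown, and a slower peritoneal profile would reduce the contrast. Re-dosed patients would have higher and more varied 24 h levels, which changes which time is quiet but gives no reason to expect equal variances.

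For the cell assays, confidence is moderate. All-pairs error is about 5.5–10% over the assumed range. The main fault is uneven allocation: a single predose contrast runs from near 0% to 7.5%, against about 1.1% when sphericity holds, in whichever direction the spread runs.

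Importance lies between worth considering and should change.

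**What to change.** **Section 11.2.1.** Replace the ANOVA/Tukey sentence with estimation: geometric means and 95% confidence intervals for R, S and the R:S ratio at each post-dose time, with no test against a zero predose. State in advance how values below the lowest standard are handled, and report the ratio only where both enantiomers are measurable. Mark 24 h values that follow more than one dose.

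**Section 11.2.2.** Replace the sentence with three planned contrasts (1, 6 and 24 h minus predose), each with its own paired standard error, Holm-adjusted at a stated two-sided alpha. Report 48 h separately for multi-dose patients.

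The adjustment is essential: unadjusted, the three contrasts give about 13% family error in most patterns. Dunnett's test with a pooled error would repair the family of comparisons but not the error term (8.6% at SDs 1, 3, 1, 1, n=7).

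**Cost.** Wording only, with no added patients or samples. If sphericity does hold, per-contrast power at n=7 falls by about 1–2 points when all times shift, 8 when two shift and 13 when one does. At n=10 the one-time loss is about 3 points.

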11.3 Safety Analysis

Patients will be examined at each time-point for subjective/objective evidence of developing drug toxicity according to NCI-CTC toxicity criteria or complications from the blood draws or port access

12.0 SOURCE DOCUMENTS AND CASE REPORT FORM COMPLETION

12.1 Source Documents

Source documents are defined as original documents, data and records. This may include hospital records, clinical and office charts, laboratory data/information or evaluation checklists, pharmacy dispensing and other records recorded from automated instruments. Data collected during this study must be recorded on the appropriate source documents.

12.2 Case Report Forms

Case report forms (CRF) must be completed for each subject enrolled in this study. The case report forms will contain the subjects unique identifiers, demographic characteristics (age, gender, and ethnicity) and baseline characteristics, including vital signs, performance status, and histologic subtype, will be primarily descriptive. The information on the case report forms will be collected and used for data analysis.

Information obtained from subjects will be used by study staff and it will be shared with the sponsor of the study (representatives of the Department of Defense). The University of New Mexico Health Sciences Center Human Research Review Committee (HRRC) which oversees human subject research, the New Mexico Cancer Care Alliance, the UNM CC Clinical Trials Office, and the Food and Drug Administration and/or other entities that may have access will be permitted to access to records.

Study records and specimens will be assigned a code number by the study team and the subjects will not be identified by name in the study records.

Study records will be retained for 2 years following the date of study completion.

13.0 ASSESSMENT OF SAFETY

The safety of this therapy will be assessed through collection and analyses of adverse events (AEs) and laboratory tests.

13.1 Specification of Safety Variables

Safety assessments will consist of monitoring and recording protocol-defined adverse events (AEs) and serious adverse events (SAEs); measurement of clinically-specified hematology, clinical chemistry, and urinalysis variables; measurement of clinically-specified vital signs; and other clinically-specified tests that are deemed critical to the post-operative patient care plan.

13.1.1 Adverse Events

An AE is any unfavorable and unintended sign, symptom, or disease temporally associated with the use of any medication or other protocol-imposed intervention, regardless of attribution.

This includes the following:

- AEs not previously observed in the patient that emerge during the protocol-specified AE reporting period, including signs or symptoms associated with the malignancy that were not present prior to the AE reporting period
- Complications that occur as a result of protocol-mandated interventions
- If applicable, AEs that occur prior to assignment of study treatment associated with medication washout, no treatment run-in, or other protocol-mandated intervention
- Preexisting medical conditions (other than the condition being studied) judged by the investigator to have worsened in severity or frequency or changed in character during the protocol-specified AE reporting period
- Diagnoses and/or symptoms associated with malignancy should be reported as AEs if they worsen or change in character. Clinical progression of malignancy should not be reported as an AE.

13.1.2 Serious Adverse Events

An AE should be classified as an SAE if:

- It results in death (i.e., the AE actually causes or leads to death).
- It is life threatening (i.e., the AE, in the view of the investigator, places the patient at immediate risk of death. It does not include an AE that, had it occurred in a more severe form, might have caused death.).
- It requires or prolongs inpatient hospitalization.
- It results in persistent or significant disability/incapacity (i.e., the AE results in substantial disruption of the patient's ability to conduct normal life functions).
- It is considered a significant medical event by the investigator based on medical judgment (e.g., may jeopardize the patient or may require medical/surgical intervention to prevent one of the outcomes listed above).

All AEs that do not meet any of the criteria for serious should be regarded as nonserious AEs.

The terms “severe” and “serious” are not synonymous. Severity (or intensity) refers to the grade of a specific AE, e.g., mild (Grade 1), moderate (Grade 2), or severe (Grade 3) myocardial infarction. “Serious” is a regulatory definition (see previous definition) and is based on patient or event outcome or action criteria usually associated with events that pose a threat to a patient’s life or functioning. Seriousness (not severity) serves as the

guide for defining regulatory reporting obligations from the Sponsor to applicable regulatory authorities.

Severity and seriousness should be independently assessed when recording AEs and SAEs.

13.2 Methods and Timing for Assessing and Recording Safety Variables

The investigator is responsible for ensuring that all AEs and SAEs that are observed or reported during the study are recorded and reported to the sponsors (UNM CRTC) in accordance with protocol instructions. Since this protocol does not include an investigational agent, the SAE period will include the time of sample collection and 24 hours after the last collection at which time the port is de-accessed.

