1.5.4 Side Effects from Blood Tests or Intravenous Risks

Frequent blood samples will be collected during this study. The subject may experience pain, bleeding from the puncture site or in tissues surrounding the puncture site, blood clot formation, or local infection and inflammation at the puncture site (very rare). An intravenous catheter (plastic tube) will be in place for routine postoperative care and will be the site used for administration of the ketorolac. It is typical that a second IV is in place. If able, this IV will be used to draw the study samples in an attempt to avoid additional needle sticks. In the event that a second IV is not in place, the investigator will draw blood using a small needle. Bleeding at the site where the catheter is or where needle sticks are made into the skin can cause bleeding under the skin causing a bruise. There is a possibility of infection, with swelling, redness and pain at the site where the ketorolac goes into the vein. It is extremely rare but possible that a serious infection of the blood stream or the heart valves or the formation of a blood clot in the lungs. The subjects will be re-admitted to the hospital to get treatment for these rare but serious problems if they occur after hospital discharge.

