1.5.5 Side Effects from Peritoneal Port

Frequent fluid samples from the subjects' abdomen will be collected during this study. The subject may experience pain, bleeding from the puncture site at the port or in tissues

surrounding the puncture site, blood clot formation, or local infection and inflammation at the puncture site (very rare). A Huber needle is inserted in the port reservoir at the time of catheter placement in the operating room and left there during the time of the collection.. The subject may feel some irritation in abdomen during the time when the fluid is being drawn into a syringe. There is a very small possibility that they subject will develop peritonitis. This would need to be treated with antibiotics and would likely become evident during the hospitalization.

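### The SAE period closes 48 to 72 h after the first dose with no later contact, although the protocol foresees serious study-procedure complications after discharge

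*Combined protocol and SAP*

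**What the plan says.** **SAE period.** Section 13.2 sets it in one sentence: "the SAE period will include the time of sample collection and 24 hours after the last collection". The sentence ends by linking this to the de-accessing of the port. The reason given is in the same sentence: "Since this protocol does not include an investigational agent".

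**Sampling times.** Section 10.2 schedules post-dose collections at 1, 6 and 24 h. A further "48 hour sample (after the initial dose) will be done in patients having elective multiple ketorolac dosing".

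**Foreseen complications.** Section 1.5.4, on the risks of the blood tests and the IV, calls it extremely rare but possible that there is "a serious infection of the blood stream or the heart valves or the formation of a blood clot in the lungs". It goes on: "The subjects will be re-admitted to the hospital to get treatment for these rare but serious problems if they occur after hospital discharge".

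**Definitions.** Section 13.1.1 counts complications of protocol-mandated interventions as AEs. Other items in the same list depend on a protocol-specified AE reporting period. Section 13.1.2 makes any AE that requires inpatient hospitalization serious.

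**Assessment and oversight.** Sections 11.3 and 13.2.1 tie safety assessment to the evaluation time points. Section 13.2.2 gives the independent monitor authority over suspension on the basis of ongoing safety review. Monitoring is continuous for the first three patients and at least quarterly after that.

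**The concern.** The protocol describes a class of serious event that it expects could appear after the patient has gone home. It then sets a collection period that will normally have ended by that time. The two statements do not fit together, and nothing else in the document bridges them.

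The justification for the short period concerns the drug. Much of what the study adds to routine care is procedural: repeated blood sampling, and a needle kept in the peritoneal port so that fluid can be drawn. Section 11.3 makes complications of exactly these procedures part of the safety analysis. A period justified by the status of ketorolac leaves that procedural risk without an argued follow-up.

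At stake is the completeness of the safety record and of what the monitor is required to receive. If late events are left out, the recorded count can only be too low.

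**Working it through.** The plan states no numerical figure to reproduce. The check is a short calculation of the window and a comparison of sections.

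**1. Length of the window.** Inputs: last scheduled sample (Section 10.2) and the 24 h extension (Section 13.2).
- Single dose: 24 h + 24 h = 48 h after the dose.
- Multiple doses: 48 h + 24 h = 72 h after the first dose.

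**2. Observation after the needle is removed.** Section 13.2 can be read in two ways. If the port is de-accessed at the end of the window, no SAE observation follows needle removal. If it is de-accessed at the last collection, 24 h follow.

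**3. One event traced through the document.** Take a bloodstream infection from a study blood draw that begins after discharge and leads to re-admission.
- Section 1.5.4: foreseen.
- Section 13.1.1: an AE, as a complication of a protocol-mandated intervention. That item has no time limit.
- Section 13.1.2: serious, because it requires hospitalization.
- Section 13.2: outside the SAE period if it starts more than 48 h (or 72 h) after the first dose.
- Sections 11.3 and 13.2.1: no scheduled assessment at which it would be sought. The last is the 24 h or 48 h sample.

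**4. Search for something that closes the gap.** The AE reporting period in Section 13.1.1 has no stated length. Section 9.3 mentions follow-up, but none is defined. No later visit, call or record check appears.

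**5. Where discharge falls.** The discharge day is not given. The needle stays in the port during collection (Section 1.5.5), so a patient is presumably in hospital at least until the last sample. Discharge would then usually fall close to or after the end of the window.

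**6. How often this could matter.** The documents give no event rate, so one has to be assumed. With per-patient risk p and n patients, the chance that at least one such event occurs is 1 − (1 − p)^n. Section 11.2.1 expects 7–10 complete sample sets out of 25 patients with ports; the number exposed to study procedures lies somewhere in that range.

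| n | p = 1% | p = 5% |
|---|---|---|
| 7 | 6.8% | 30.2% |
| 10 | 9.6% | 40.1% |
| 25 | 22.2% | 72.3% |

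The 5% column is hard to square with an event called extremely rare. The figures count events at any time, inside or outside the window, so they are ceilings on the chance of missing at least one.

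**The case against.** The strongest reply is that this is a wording gap with little practical consequence. Several parts of it stand.

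- **Late reports are not barred.** Section 13.2 first requires reporting of all AEs and SAEs observed or reported during the study, and Section 13.2.1 covers events volunteered or found by other means. Section 14 adds a duty under GCP and local law. Patients come from the investigators' own practices (Section 7.0), so a re-admission may well become known. This stands, but none of it prompts anyone to look, and the end of study for a subject is undefined.
- **The monitor.** A reader might infer that the monitor is blind to these events. The documents do not support that: review continues at least quarterly, under an institutional plan not reproduced here. They support only that delayed events need not be reported to the monitor.
- **Peritonitis.** A reader might add the port risk in Section 1.5.5: "There is a very small possibility that they subject will develop peritonitis". That section goes on to expect it to show itself during the hospital stay, so it is not evidence of a post-discharge gap. The case rests on Section 1.5.4.
- **Attribution.** The IV used for dosing is in place for routine care, and the port must be clinically indicated. After major surgery, a late infection or clot may be hard to attribute to study procedures. This stands and limits what the extra data can show.
- **The drug itself.** With an R-enantiomer half-life of about 5 h (Section 1.5.2), 48 h after a single dose is 48/5 = 9.6 half-lives. The argument for longer collection is therefore stronger for the procedures than for ketorolac.
- **A safety rate.** A reader might divide one missed event by the 7–10 complete sets, or quote an upper bound for zero events. Complete sets are not the number exposed. A zero-event bound depends only on sample size and would be the same after the fix. The plan also estimates no safety rate.

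**Conclusion.** The concern holds in a limited form. Section 13.2 closes the SAE period at 48 or 72 h, Section 1.5.4 foresees serious study-related complications after discharge, and no scheduled contact connects the two. Such events would not be actively collected. The absence of an investigational agent does not justify this for the blood draws and port access.

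Two assumptions carry the conclusion. First, discharge usually falls near or after the end of the window; a patient discharged earlier could have a post-discharge event inside it. Second, the institutional monitoring plan does not itself require later follow-up.

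The likely effect is small. At an assumed 1% risk, the chance that any such event occurs at all is about 7% to 22%, depending on how many patients are exposed. The primary pharmacokinetic endpoint is unaffected. The point is worth acting on because a stated rule leaves out complications that the protocol itself names, and correcting it is cheap.

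**What to change.** Reconcile Sections 1.5.4, 13.1.1 and 13.2:

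1. Give the AE reporting period in Section 13.1.1 an explicit start and end.
2. In Section 13.2, keep the present short window for events judged unrelated to the study. Collect SAEs possibly related to study blood draws, study port access or ketorolac up to one fixed later contact that already exists in routine care. The sponsor chooses which contact.
3. State that the check is made by chart review or telephone call, and that any event found is reported to the sponsor and the independent monitor.
4. State whether the port is de-accessed at the last collection or 24 h later, so that the period after needle removal is clear.

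The cost is a short amendment to the text, one chart check or call per patient, and a few more SAE forms. Some of the added events will be hard to attribute after major surgery, so causality should be recorded as possibly related where it cannot be settled. Treatment, sampling and the primary analysis do not change.
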